STUDY PROTOCOL & ANALYSIS PLAN

Protocol Title: A Novel Parent Education Program for Early Intervention
Grant Number: 2U54GM104941-06
Clinical Trials ID: NCT04266717
Date of Document: September 15, 2022

Principal Investigator

Name: [name], PT, PhD
Department/Center: Physical Therapy Department, University of Delaware
Contact [contact]
Email Address: [contact]

PURPOSE

The purpose of this pilot clinical trial is to determine whether parent education impacts daily parent-infant handling and positioning activity or infants' developmental outcomes.

PARTICIPANTS

We will enroll twenty participants 1-5-months-old who are not yet rolling and are of any gender. To be included, infants and their parents must be able to safely and independently engage in the data collection activities and be available for data collections. Infants with medical equipment that restricts movement or positioning will not be included. Infants who are blind will also be excluded. Participants will be recruited via advertisement in the local community.

Participation in the study is voluntary and there is no compensation for participation. During the first contact made with potential participants, written information explaining the study will be provided that details in simple terms, a) criteria for participation, b) purpose of the research and procedures involved, c) right to withdraw at any time without penalty of any kind, and d) assurance of confidentiality (via number ID representation vs. name). If the individual meets the criteria for participation and is interested, the information just described will be reviewed, questions will be answered and an informed consent form will be signed in the presence of a witness. Parents of the participants will be reminded by the researcher that this signature does not bind them to participate and that they are free to withdraw at any time.

PROCEDURES

This study will involve 3 data collections that occur in the home. Informed consent will be obtained prior to the first data collection. Parents will be provided the opportunity to read the consent form, the contents will be reviewed with the family, and any questions or concerns will be discussed prior to obtaining consent.

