After families consent, they will be asked to complete a Health & Demographic Form. Based on the information in this form, infants will be assigned to one of 4 risk categories: No health or socioeconomic risk; Only health risk; Only socioeconomic risk; or Health *and* socioeconomic risk. Health risk will include infants who were born very preterm, infants who had a documented neurologic or respiratory problem at birth, and infants who spent more than 1 week in the neonatal intensive care unit after birth. Socioeconomic risk will include infants whose families report combined income levels below poverty level or report middle or high school completion as the highest level of parental education. Blocked random assignment will then be performed within risk categories so that infants are assigned to the Milestone Education Group or the Positioning Education Group.

The total time commitment for participants in this study involves three data collections 30-75 minutes in duration; the baseline data collection happens at the time families enroll with infants at 1-5 months of age and the second data collection happens one month later. Families will also be asked to allow researchers to contact them monthly to collect milestone attainment data through the time infants begin walking independently (typically occurs between 10 and 18 months of age). The final data collection will happen when infants are between 16 and 24 months of age.

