The first data collection will begin with infants donning the Get Around Garment, a smart garment that collects valid, reliable data about the position of infants (i.e., supine, reclined, upright, inclined, or prone). Then, the data collection will consist of: 1) one 2.5-minute *Structured Play Assessment* during which the infant will be placed by the experimenter for 15-30 seconds into each of the following 5 positions: supine, prone, inclined about 45 degrees from upright, reclined about 45 degrees from upright, and seated upright; 2) one 60 minute *Free Play Assessment* during which parents will be encouraged to go about their typical daily activities as if the experimenter were not there; and 3) a second 2.5-minute *Structured Play Assessment*. Accelerometer data from the garment will be collected simultaneously with video data throughout these assessments. Accelerometer data will be saved on a memory card or transmitted to a research computer via Wi-Fi. The entire visit will be video recorded. By comparing data from the garment and the video throughout the entire visit within each infant, we can determine whether the garment provides valid position data throughout the wearing session. The garment will be left with families, and they will be asked to have their infants wear it for 2 days during awake periods when with an adult but not during periods of sleep or periods without supervision. Families will be asked to log the times the sensor belt was worn and infants' general activity. Sensor data will be stored so we can better understand infants' activity across a typical 2-day period. We will leave 2 garments just in case one gets dirty. We will inform families they can wash the garments as they would typical clothing except that they should first remove the sensor unit. Note that garments that are in good condition (no stains) may be re-used for other babies after we wash them. After the 2-day period, the researchers will collect the garment from the family, will collect the Sensor Wearing Log and ensure the data on the log are complete and correct, and will ask parents to complete the Garment Perception Survey. They will also assess infants using the Alberta Infant Motor Scale and the Bayley Scales of Infant Development III to show their developmental abilities at the start of the study.

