The second data collection will occur after a 4-week period of requested daily activity engagement according to the education received. The researchers will collect the Activity Logs and ensure data on them is complete and correct. Then the researchers will repeat all procedures from the first data collection, as described above, including a second, 2-day wearing period for the garment. Parents will be informed that daily activity engagement is no longer expected. At this data collection, parents will be taught how to keep track of their infant's milestones using the Milestone Checklist. The research team will contact families monthly through the onset of walking (typically between 10-18 months of age) to gather information about infants' performance on this checklist.

The third and final data collection will serve as a follow-up visit when infants are 16-24 months of age. Infants will be assessed using the Alberta Infant Motor Scale to show how their developmental abilities have changed since the start of the study and whether there are differences between the two education groups. Parents will be asked to complete the Dimensions of Mastery Questionnaire (DMQ 18) to evaluate each child's intrinsic motivation to move and explore so we can determine if and how this relates to our early measures of development and interaction.

RISKS AND BENEFITS

The risks associated with participation in this study are minimal. The assessment procedures are safe, and are similar to movement and play activities experienced by infants on a regular basis. The measurements are non-invasive, play- or functionally-based, and have been used in past research with infants.

There is a risk that participants may experience fatigue or be upset during the visits. If the infant cries or shows facial expressions suggesting fatigue or upset, we will take a break from the activities. We will not continue again until the infant has his/her needs met (sleeping, eating, diaper changing, etc) and appears happy and eager to join the testing again based on his/her affect and facial expressions. We will reschedule for another time if that better meets the infant's and family's needs.

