The garment could be uncomfortable for infants. The sensor unit could rub the infant's skin. The garment has been designed with the sensor unit on the lateral aspect of the infant's trunk since infants do not typically place weight on this part of their body before they begin rolling over. Infants will not be enrolled in the study if they are already rolling. In addition, the sensor unit is quite small (2.44" long x 1.47" wide x 0.7" thick) so should not interfere with parents carrying infants. Researchers will check and parents will be asked to check infants' skin for redness after removing the garment. If we note irritation or redness that lasts more than 20 minutes, we will work on better fitting the garment and sensor. If the problem persists for an infant, we will discontinue that aspect of the experiment for that infant.

The sensor unit is made of small parts and uses a low level battery for energy supply. These parts could cause a choking risk if exposed. The garment is designed so that the sensor unit is secured within a 3D printed case, which is housed within a snug fabric enclosure to avoid small parts of the sensor unit from breaking off. As an added precaution, the garment will be used under the supervision of researchers or under the advised supervision of parents in the home.

Infants and parents may benefit from receiving education on development and learning the results of infants' developmental assessments.

Early handling, positioning, and play activities have been linked to future motor and cognitive abilities. It is helpful to understand the ways infants and parents are engaging in early movement activities and

how we can change those practices to positively impact development, especially for infants with health or socio-economic risks.

DATA ANALYSIS PLAN

All assessments and data coding will be conducted by trained experimenters masked to group assignment. Coders will be trained to ensure they are reliable before conducting official data coding. 20% of all data will be recoded to ensure high levels of intra- and inter-rater reliability are maintained. Double data entry will be conducted where applicable.

Primary outcome: To determine whether the change in AIMS score from Visit 1 to 2 differs between the two education groups, Wilcoxon tests will be performed for intra-group, Mann-Whitney for inter-group comparisons, with Bonferroni corrections.

Secondary outcomes:

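### Does the second 2-day garment wear need a rolling check, given that the side-of-trunk sensor placement is explained by infants not yet rolling?

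*Combined protocol and SAP*

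**What the plan says.** Three parts of the combined protocol and SAP bear on this.

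- **Entry.** PARTICIPANTS plans to enrol "twenty participants 1-5-months-old who are not yet rolling". RISKS AND BENEFITS repeats the condition: "Infants will not be enrolled in the study if they are already rolling".
- **Reason for the placement.** RISKS AND BENEFITS names discomfort and rubbing of the skin as garment risks. It gives the lateral position as a design response, "since infants do not typically place weight on this part of their body before they begin rolling over".
- **Second wear.** PROCEDURES says that "the second data collection happens one month later". On that occasion, "Then the researchers will repeat all procedures from the first data collection, as described above, including a second, 2-day wearing period for the garment".

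PROCEDURES also fixes the order within a data collection. The infant puts on the garment and goes through a structured play segment, a free play hour and a second structured segment. The garment is then left with the family. The Alberta Infant Motor Scale (AIMS) and the Bayley assessment are described at garment collection, after the two days. The Milestone Checklist is first taught at the second data collection.

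The safeguards are wear only while awake and with an adult (PROCEDURES), and skin checks after removal, refitting if irritation or redness lasts more than 20 minutes, and discontinuation if the problem persists (RISKS AND BENEFITS).

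**The concern.** The placement argument is about infants who do not yet roll. That status is established once, at entry, but the garment goes home twice, about a month apart. The plan itself expects motor change in that month. Its primary outcome is AIMS change from Visit 1 to Visit 2, and the positioning and play activities are described as having advanced development in earlier work. Some infants may therefore be rolling by the second wear, and for them the stated reason for the sensor position would be weaker.

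No later step clearly fills the gap. In the described order, the motor assessments come after the second wear, and so do the monthly milestone contacts. Staff watch the infant in the garment before leaving it, but nobody is asked to note rolling and no action depends on it.

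What would be at stake is minor skin rubbing or discomfort over up to two days at home. There is no evident route to bias in the comparison of the two education groups.

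**Working it through.** The plan states no rate, power or sample-size figure on this point, so there is none to reproduce. The check is simple arithmetic on timing and a reading of the relevant sections together.

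**Inputs**

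| Input | Value | Where |
|---|---|---|
| Infants enrolled | 20 | PARTICIPANTS |
| Age at entry | 1 to 5 months | PARTICIPANTS |
| Interval to second data collection | about 1 month | PROCEDURES |
| Structured play | 2 segments of 2.5 minutes | PROCEDURES |
| Free play | 60 minutes | PROCEDURES |
| Time per placed position | 15 to 30 seconds | PROCEDURES |
| Rolling rate, skin-reaction rate | not given | – |

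**Age at the second wear.** (1 to 5) + 1 = about 2 to 6 months. The screening information is about one month old by then.

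**Attended observation before the garment is left.** 2.5 + 60 + 2.5 = 65 minutes in the garment. PROCEDURES adds that "The entire visit will be video recorded".

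**Experimenter-placed supine and prone time.** In each structured segment the infant is "placed by the experimenter for 15-30 seconds into each of the following 5 positions: supine, prone" and three others. Two segments × 2 positions × 15 to 30 seconds = 60 to 120 seconds, or 1 to 2 minutes. This is a poor measure of the chance to see rolling. It leaves out the free play hour, "during which parents will be encouraged to go about their typical daily activities as if the experimenter were not there", and nothing in the plan keeps the infant off the floor during that hour. The relevant figure is nearer the full 65 minutes.

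**Infants affected.** With no rolling rate, the count lies between 0 and 20, each with up to 2 home-wear days. That range is the whole sample and includes none, so it cannot support a claim of harm.

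**Do the sections conflict?** The placement sentence carries the qualifier *typically* and explains a design choice. The sentence after it is expressly about who may enrol. Neither makes non-rolling a condition of wearing the garment, so the second wear breaches neither.

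**Does any safeguard lapse at the second wear?**

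| Safeguard | Depends on rolling? | Limited to the first wear? |
|---|---|---|
| Awake wear with an adult | No | No |
| Skin check after removal | No | No |
| Refitting | No | No |
| Discontinuation if the problem persists | No | No |

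The plan monitors the harm itself. Rolling is only an indirect marker for it.

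**What would a check add?** Suppose a yes/no item is recorded with no action attached. No analysis in the DATA ANALYSIS PLAN uses it, and no infant is managed differently. Suppose instead that a rule restricted wear for rolling infants. Second-wear sensor data would then be lost according to motor development, which the interventions are meant to influence, so the loss could differ between groups. Change in positioning practices from Visit 1 to Visit 2, measured by the sensor, is a secondary outcome. Assuming an even split, each group has 20 / 2 = 10 infants, so losing one infant costs 1 / 10 = 10% of that group's data.

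**The case for a change.** The best argument for acting is that the item is cheap and uses contact already planned. One question could be asked when the Activity Logs are collected, helped by what staff see during play, and one paragraph reworded. A preventive reason that is written down ought to hold whenever the device is worn, or the text should say what applies when it does not. Skin checks come after removal, so they detect irritation but do not prevent it. The infants are young and the wear takes place at home.

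Much of this stands. The plan states no check before the second wear, the motor assessments do come too late in the described order to serve as one, and detection is not the same as prevention.

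Two parts do not carry through. First, the item prevents something only if a rule follows from it, and such a rule brings the missing-data cost shown above. Second, the cost is not quite nil even for the question alone. PROCEDURES keeps the assessor masked and reminds parents not to discuss their group. A milestone question asked while activity logs change hands, before the AIMS is scored, could prompt talk that reveals the group. A yes/no answer does not itself disclose assignment, and having someone other than the masked assessor ask would avoid the difficulty, so this cost is conditional and small. The benefit is also small, and the documents cannot show that it is above zero.

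**Conclusion.** No change to the plan is needed. The observation is accurate: rolling is screened at entry only, and the second wear comes about a month later at about 2 to 6 months of age with no stated re-check. But it identifies neither a contradiction nor a harm left without a safeguard, and it has no bearing on the primary comparison.

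Its size cannot be put more tightly than 0 to 20 infants with up to 2 days each, because the documents give neither a rolling rate nor a skin-reaction rate. The conclusion assumes that the supervision, skin-check, refitting and discontinuation provisions apply to the second wear as to the first. The text supports this, since it repeats all first-visit procedures and does not limit the provisions in RISKS AND BENEFITS to one visit. It also assumes that the risk concerned is the one the plan ties to placement, namely rubbing and discomfort.

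If the document is being revised for other reasons, the sponsor could make the placement sentence cover both wears. That is editorial. How infants who have begun rolling are handled is for the sponsor and investigator to decide.

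### The primary Mann-Whitney test on one-month AIMS change adjusts for neither age nor baseline AIMS, so a chance age gap between arms of about 10 infants goes uncorrected and precision may be lost

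*Combined protocol and SAP*

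**What the plan says.** - **Data Analysis Plan, primary outcome.** The aim is "To determine whether the change in AIMS score from Visit 1 to 2 differs between the two education groups". The method is "Wilcoxon tests will be performed for intra-group, Mann-Whitney for inter-group comparisons, with Bonferroni corrections". No covariate, stratified test or age-referenced score is named.
- **Participants.** "We will enroll twenty participants 1-5-months-old who are not yet rolling and are of any gender". No sample-size reasoning accompanies the number. Risks and Benefits repeats the restriction: "Infants will not be enrolled in the study if they are already rolling".
- **Procedures, allocation.** "Blocked random assignment will then be performed within risk categories". The four categories combine health risk and socioeconomic risk. Age and baseline motor score play no part, and the allocation ratio and block size are not given.
- **Procedures, first data collection.** "They will also assess infants using the Alberta Infant Motor Scale and the Bayley Scales of Infant Development III". A baseline Alberta Infant Motor Scale (AIMS) score therefore exists for use as a covariate. Visit 2 follows about four weeks later.

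**The concern.** Entry ages span four months, while the primary outcome is the gain over about one month. Subtracting baseline AIMS uses it with a fixed slope of 1. It does not remove any dependence of the gain itself on age or starting level. If the gain varies with age, a chance difference in mean age between two small arms moves the observed group difference even when the education has no effect. The planned analysis has no means of allowing for this, and an adjustment added after seeing the imbalance would be post hoc.

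The same unexplained variation also widens the uncertainty in a trial of only 20 infants. If age and baseline barely predict the gain, little is lost. The documents do not say how strong the relation is, or whether the AIMS score is raw or age-referenced.

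**Working it through.** **Inputs from the documents.** 20 infants; entry at 1-5 months, not yet rolling; Mann-Whitney test on AIMS change; about four weeks between visits; stratification by risk category only.

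**Assumptions, none stated in the documents.** 10 v 10 infants; ages uniform on 1-5 months; normally distributed residuals; no dropout; two-sided 0.05 before any Bonferroni division; age-change correlation r of 0, 0.3, 0.5 or 0.7; age-baseline correlation 0.8, with baseline AIMS adding nothing beyond age.

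**Step 1: the plan's own figure.** The only figure is the total of 20. It comes with no alpha, effect size, SD or power, so there is no calculation to reproduce. For scale, with 10 per arm the effect detectable at 80% power (normal approximation) is (1.960 + 0.842) × √(2/10) = 1.25 SD.

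**Step 2: how large a chance age gap is likely.** SD of the difference in mean age = SD(age) × √(2/10).
- Ages 1-5: (4/√12) × √0.2 = 1.155 × 0.447 = 0.516 month.
- Ages 1-4, an illustration of how the rolling exclusion might narrow the range: (3/√12) × √0.2 = 0.387 month.

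| Age distribution | P(gap > 0.5 month) | P(gap > 1 month) |
|---|---|---|
| Uniform 1-5 | 0.335 | 0.052 |
| Uniform 1-4 | 0.198 | 0.009 |
| Triangular 1-5, mode 3 | 0.17 | 0.006 |

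**Step 3: shift in the estimate.** Expected shift = r × gap / 1.155, in SDs of change. For a 0.5-month gap this is 0 / 0.13 / 0.22 / 0.30 SD at r = 0 / 0.3 / 0.5 / 0.7.

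**Step 4: false-positive rate with no true effect.** 60,000 simulated trials per setting, exact Mann-Whitney (reject when the smaller U is 23 or less; exact size 0.0433).

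| | r = 0 | 0.3 | 0.5 | 0.7 |
|---|---|---|---|---|
| Mann-Whitney, all trials | 4.4% | 4.5% | 4.2% | 4.2% |
| Mann-Whitney, gap > 0.5 month | 4.3% | 5.8% | 7.4% | 10.1% |
| Mann-Whitney, gap > 1 month | 4.8% | 7.6% | 15.0% | 27.3% |

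ANCOVA on age and baseline stays at 4.8-5.4% under the same conditions.

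**Step 5: power for a true 1.0 SD effect.** 40,000 simulated trials per setting.

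| | r = 0 | 0.3 | 0.5 | 0.7 |
|---|---|---|---|---|
| Mann-Whitney (planned) | 51.2% | 50.8% | 50.7% | 49.9% |
| Unadjusted t-test | 56.0% | 55.8% | 55.9% | 56.1% |
| ANCOVA, age + baseline | 50.6% | 54.5% | 62.9% | 79.3% |
| Rank ANCOVA, age + baseline | 49.9% | 52.7% | 59.6% | 73.8% |
| ANCOVA plus two risk indicators | 49.5% | 53.3% | 61.4% | 78.0% |

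**Step 6: when adjustment pays.** Variance relative to the unadjusted estimate = (1 − R²) × (1 + q/(N − q − 3)). With N = 20 and q = 2 the second factor is 1 + 2/15 = 1.133.
- R² = 0: 1.13
- R² = 0.25 (r = 0.5): 0.85
- R² = 0.50: 0.57
- Break-even: R² = 1 − 1/1.133 = 0.12, or r of about 0.34.

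This agrees with Step 5: at r = 0.3 two-covariate ANCOVA does not beat the unadjusted t-test, and at 0.5 it does.

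**The case against.** The strongest reply is that this is a question of efficiency, not of error. Randomisation keeps the Mann-Whitney test valid (4.2-4.5% overall), the change score already uses baseline, and a rank test is a reasonable choice for a pilot. That stands, and the concern does not claim bias.

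Other points with some force:

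- **The conditional rates show one side only.** If error rises when the gap is large, it must fall when the gap is small. From Step 4, the rate for gaps of 0.5 month or less at r = 0.5 is (4.2 − 0.335 × 7.4)/0.665 = 2.6%. Direct simulation gives about 4%, 3% and 1.5% at r = 0.3, 0.5 and 0.7. The 27% case arises in few trials, and false positives from it in 0.052 × 0.273 = 1.4% of all trials at r = 0.7.
- **Bonferroni is ignored.** At 0.0167 (three tests, an assumption), the Mann-Whitney rate given a gap above 1 month is 3.2%, 6.4% and 14.2% at r = 0.3, 0.5 and 0.7. These are lower in absolute terms, but relative to the nominal 1.67% they are about 1.9, 3.8 and 8.5 times too high. The power advantage of ANCOVA persists at that level.
- **At r = 0.3 the gain over Mann-Whitney comes from the type of test, not from adjustment.** This is correct: the unadjusted t-test does slightly better there.
- **Age alone would do better in this simulation** (54%, 57%, 66% and 82% power). True, because the model assumes baseline AIMS adds nothing beyond age. That assumption counts against the two-covariate model; it is not evidence that baseline is useless.
- **An age-referenced score could weaken the correlation.** Possible, and the plan does not define the score.

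These points limit the weight of the concern. They do not remove it: compared with the planned test, adjustment loses essentially nothing even at r = 0 (50.6% v 51.2%).

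**Conclusion.** The concern holds as a recommended improvement, with medium confidence. Neither the stratification nor the primary analysis accounts for age, and baseline AIMS is subtracted but not modelled. The planned test is valid on average. What it lacks is protection against the imbalance that this one trial happens to realise, together with any precision that age and baseline could supply.

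The size depends on an age-change correlation that the documents do not give. At 0 there is nothing to gain. At 0.3 the gain over Mann-Whitney is 54.5 − 50.8 = 3.7 points of power. At 0.5 it is 62.9 − 50.7 = 12.2 points, and at 0.7 it is 79.3 − 49.9 = 29.4 points. The chance of a material age gap is likewise conditional: 34% for more than 0.5 month if ages fill the 1-5 month window evenly, and 17-20% if they are more concentrated. Equal arms of 10 are inferred, and small risk strata with an unstated block size could leave the arms unequal.

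**What to change.** Prespecify, as the primary between-group analysis, an ANCOVA of Visit 2 AIMS on group, baseline AIMS and age at Visit 1, using corrected age for preterm infants. A rank ANCOVA with the same covariates is an acceptable alternative if a nonparametric primary is preferred. Name one of the two before outcomes are seen by group. State whether the AIMS score is raw or age-referenced. If ANCOVA is chosen, report the adjusted difference with a 95% CI.

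Keep the Mann-Whitney test on change as a sensitivity analysis. Add a second sensitivity analysis that also includes the health-risk and socioeconomic-risk indicators used to form the randomisation categories. If they are not prognostic, these cost a further 1-1.5 points of power (Step 5).

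The cost is wording in the analysis plan and two degrees of freedom. Baseline AIMS is already collected, and age is needed for eligibility. Corrected age also needs gestational age at birth. The Health & Demographic Form is used to identify very preterm infants, but its fields are not shown, so confirm that it records gestational age. The downside is little or no gain if age and baseline barely predict change.

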To determine whether changes in parent-child interaction behavior or positioning practices (sensor data) differ from Visit 1 to 2 between the two education groups, Wilcoxon tests will be performed for intra-group, Mann-Whitney for inter-group comparisons, with Bonferroni corrections.

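### The primary between-group test shares a Bonferroni correction with within-group tests that cannot answer the primary question, and no alpha or family is stated

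*Combined protocol and SAP*

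**What the plan says.** The Data Analysis Plan gives the primary outcome one sentence. It opens with the question: "To determine whether the change in AIMS score from Visit 1 to 2 differs between the two education groups". The question runs straight on into the methods, so that the sentence asks whether the change "differs between the two education groups, Wilcoxon tests will be performed for intra-group, Mann-Whitney for inter-group comparisons, with Bonferroni corrections".

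The secondary outcomes have their own entry. Its question is "To determine whether changes in parent-child interaction behavior or positioning practices (sensor data) differ from Visit 1 to 2", and the method wording is the same: "between the two education groups, Wilcoxon tests will be performed for intra-group, Mann-Whitney for inter-group comparisons, with Bonferroni corrections".

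The Participants section sets the size: "We will enroll twenty participants 1-5-months-old who are not yet rolling and are of any gender". On allocation, the Procedures section says "Blocked random assignment will then be performed within risk categories", with no ratio or block size.

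The document gives no significance level, sidedness, Bonferroni divisor, effect size, standard deviation or power target.

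**The concern.** The primary question is a single contrast between two groups. A Wilcoxon signed-rank test within one group asks whether that group's scores moved over a month; it carries no information on whether the groups moved by different amounts. Two such tests, one per group, therefore add nothing to the primary inference.

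The Bonferroni clause nevertheless follows a list that includes them. Correcting a single test would have no effect, so the clause reads most naturally as covering the set: two Wilcoxon tests and one Mann-Whitney. On that reading the test that matters pays for two that do not. The price is power, in a trial of 20 infants that has little to spare.

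Because neither alpha nor the family is written down, the threshold for the primary result is also not fixed in advance. At an assumed alpha of 0.05, a Mann-Whitney p-value of 0.03 would be positive if that test stands alone and negative if three tests share the correction.

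**Working it through.** There is no stated power figure or threshold to reproduce, so the check sets the two main readings side by side.

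**Inputs from the document**
- Total sample: 20 infants (Participants).
- One between-group contrast on AIMS change, Visit 1 to Visit 2 (Data Analysis Plan, primary outcome).
- Tests: Wilcoxon within each of two groups, Mann-Whitney between groups, Bonferroni corrections (same sentence).

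**Inputs assumed**
- Two-sided family alpha of 0.05.
- Equal allocation, 10 v 10.
- Normal change scores with equal spread and no ties.
- True group differences of 0.5 to 1.65 SD of the change score, to show a range.

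**Step 1: count the tests.** Two groups give two Wilcoxon tests; one contrast gives one Mann-Whitney. 2 + 1 = 3.

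**Step 2: per-test threshold.** Bonferroni threshold = alpha / m.
- m = 1: 0.05 / 1 = 0.05
- m = 3: 0.05 / 3 = 0.0167

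**Step 3: exact Mann-Whitney cut-off, 10 v 10.** Two-sided p = 2 × P(U ≤ u) under the null. The largest u that keeps p within the threshold is:
- m = 1: U ≤ 23, attained level 0.0433
- m = 3: U ≤ 18, attained level 0.0147

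**Step 4: power.** This is the proportion of simulated trials (200,000 per setting) in which U reaches the cut-off.

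| True difference (SD of change) | Mann-Whitney alone (0.05) | Three tests (0.0167) | Loss in points |
|---|---|---|---|
| 0.5 | 16.1% | 7.6% | 8.5 |
| 0.8 | 35.4% | 20.2% | 15.2 |
| 1.0 | 51.4% | 33.3% | 18.1 |
| 1.2 | 66.9% | 48.6% | 18.3 |
| 1.4 | 80.2% | 64.0% | 16.2 |
| 1.65 | 91.1% | 80.2% | 10.9 |

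The difference needed for about 80% power thus rises from 1.40 SD to 1.65 SD.

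**Step 5: sensitivity to the split.** The allocation ratio is not stated. At 1.0 SD, 9 v 11 gives 52.1% and 33.8%, and 8 v 12 gives 51.1% and 32.6%. The loss is about 18 points in each case.

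**Step 6: the other readings.** If the correction applies only to the two Wilcoxon tests, the Mann-Whitney stays at 0.05 and the loss is zero. If primary and secondary outcomes are pooled, the divisor exceeds 3 and the loss is larger. It cannot be computed, because the secondary entry does not say how many interaction or positioning variables will be tested.

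**The case against.** The strongest reply is that nothing here is invalid. Bonferroni over all listed tests is conservative, the within-group tests are plainly labelled as such, and the trial is a 20-infant pilot with no power target. Uncorrected, it has only about 16% power at 0.5 SD and 51% at 1.0 SD, so it is weak on any reading. All of that stands, and it is why the point is minor. It does not remove the point: the plan names a primary outcome and a formal test, and the correction can only weaken that test.

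Four stronger readings may tempt a reader, and the document does not support them.

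- *The Mann-Whitney input is left open, so it may be run on scores at each visit.* The same sentence names the change in AIMS as the quantity to be compared between groups. Change scores are implied; the plan only omits to tie them to the test.
- *The threshold has a calculable lower limit once the secondary outcomes are pooled.* The primary and secondary entries stand under separate headings, each with its own Bonferroni clause, which favours correction within an outcome. If they were pooled, the number of variables is not given, so no limit follows.
- *The plan would infer a group difference from significance in one arm only.* It does not say so; it assigns the between-group comparison to the Mann-Whitney.
- *False positives are inflated.* Bonferroni does not do that. The possible cost is power.

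**Conclusion.** The point holds as a minor one. The plan poses one between-group question, and only the Mann-Whitney on change scores answers it, yet the stated correction covers a set that includes within-group tests, with no alpha or family given.

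On the three-test reading the loss is about 8 points of power at 0.5 SD, 18 at 1.0 SD and 16 at 1.4 SD, and nothing is gained for the primary question. These figures rest on an assumed two-sided 0.05, a 10 v 10 split and normal change scores; the effect sizes are illustrative because the document gives none. The loss runs from zero, if the correction does not reach the Mann-Whitney, to an unquantified larger amount if outcomes are pooled. No figure in the plan is wrong. This is a cheap improvement.

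**What to change.** In the primary-outcome entry, state that the Mann-Whitney test on AIMS change (Visit 2 minus Visit 1) is the single primary test, at two-sided 0.05, without Bonferroni correction. State that the within-group Wilcoxon results are supporting only and sit outside any multiplicity family.

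In the secondary-outcomes entry, list the between-group contrasts on interaction and positioning, and limit any Bonferroni family to those, separate from the primary test.

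The cost is two or three sentences in the analysis plan. No extra infants, visits or data are needed. The one downside is that the within-group p-values lose confirmatory status.
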